## 8.8 Withdrawals and Loss to Follow-Up

m If an in-window telephone visit prompts an in-person visit that, for scheduling reasons, cannot not performed within the 30-day window, no protocol deviation will be reported. Any abnormalities detected at a late 30-day in-person visit will be assigned to the 30-day visit timepoint.

Study participation is completely voluntary, and each subject is free to withdraw from the study at any time. An investigator also has the right to withdraw the subject from the study in the event of reasons concerning the health or well-being of the subject, or in the case of lack of cooperation. Should a subject decide to withdraw for any reason, or should the investigator decide to withdraw the subject, all efforts will be made to complete and report the observations up to the time of withdrawal as thoroughly as possible. A complete, final evaluation at the time of the subject's withdrawal must be made and an explanation given as to why the subject is withdrawing or being withdrawn from the study.

The reason for and date of withdrawal must be recorded on the subject's End of Study eCRF. If the reason for the withdrawal is a device- or procedure-related AE, the event must be reported to the Sponsor and recorded on the eCRF.

If the procedure is aborted, the subject does not need to complete the follow-up assessments, unless the subject is converted to surgical repair. The subject's enrollment roster position will not be made available to other subjects.

If a subject dies during the course of the study, the Sponsor will request an autopsy provided the subject authorized an autopsy in the event of death during the course of the study. Autopsy observations should include documentation of condition of body organs and determination of device and/or procedure relationship to death.

All efforts will be made to retain subjects in order to collect data at the 30-day the follow-up visit. Due diligence in reaching the subject must be made by:

- Two documented telephone contact attempts, emails, or regular postal mail letters; and
- A certified letter

After the above attempts were made, if no response is obtained, the final evaluation of a given subject will be the last visit at which study-related procedures were performed on that subject. The End of Study eCRF page will need to be completed and communication attempts must be documented.

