Two commercially available liquid embolic agents, Onyx™ (Medtronic, Irvine, CA), and Trufill® nBCA glue (DePuy Synthes/ Johnson & Johnson, Raynham, MA) are indicated for pre-surgical resection of brain arterio-venous malformations. They have no peripheral vascular indication, though their importance, clinical utility, and use in peripheral arterial hemorrhage have been widely reported.

 These liquid agents bring unique value because they cause complete, predictable, and permanent large and middle size vessel occlusion, free of the risk of incomplete occlusion due to coagulopathy and delayed recanalization, as occurs with coils and plugs. They can also be prepared and used in a fashion that enables penetration into smaller downstream arteries and arcades distal to those that can be reached with microcatheters (i.e., embolization of multiple branches can be achieved from a single catheterization location).

BlackSwan Vascular, Inc. has developed its Lava™ Liquid Embolic System (Lava LES) to treat active hemorrhage in the peripheral arterial system. For the purposes of framing the indications for use under consideration, peripheral arteries include all arteries except those in the intracranial and intradural spaces serving the central nervous system and those of the heart.

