### 6.6.3 Completed Cases Population

The Completed Cases (CC) population will include all ITT subjects who complete 30-day follow-up. The CC population will also include ITT subjects who experience failure of the primary effectiveness endpoint prior to the beginning of the 30-day follow-up timepoint, irrespective of their length of follow-up.

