## 7.7 Missing or Incomplete Data

Every effort will be made to minimize the amount of missing data. Recognizing the difficulty of avoiding some missing data, however, data imputation methods with sensitivity imputation analyses will be carried out. Safety endpoint analyses will include all subjects experiencing at least one component of the safety endpoint or with follow-up to the lower limit of the follow-up window for the 30-day time point (i.e., the denominator will be adjusted for missing data). Target Lesions with unavailable effectiveness data will be assumed to have missing data at random and will be imputed by random selection with replacement of data from Target Lesions with complete data. The robustness of the multiple imputation outcome will be tested with a tipping point analysis encompassing all possible imputation outcomes.

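### Protocol 8.8 lets investigators withdraw subjects from the study and asks for data only up to withdrawal, so an event-free subject withdrawn before day 23 leaves both SAP primary analyses

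*Protocol*

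**What the plan says.** **Who may be withdrawn.** Protocol 8.8 lets a subject leave at any time. It also gives the investigator a "right to withdraw the subject from the study in the event of reasons concerning the health or well-being of the subject", and adds lack of cooperation as a second ground.

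**What is collected.** On withdrawal, "all efforts will be made to complete and report the observations up to the time of withdrawal as thoroughly as possible". The section also requires that "A complete, final evaluation at the time of the subject's withdrawal must be made", with the reason and date on the End of Study form. It does not mention vital status, major adverse events (MAEs), rebleeding or reintervention after that date.

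**What remains after treatment.** Lava is given at the index procedure. Protocol 1.1 describes occlusion by the marketed liquid agents as "complete, predictable, and permanent large and middle size vessel occlusion". The scheduled assessments still to come are discharge and one day-30 contact, which may be by telephone (Protocol Table 7 and 8.5).

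**Safety denominator.** Protocol 7.7 counts subjects who have an event or are "with follow-up to the lower limit of the follow-up window for the 30-day time point". SAP 3.4.1 sets that limit at day 23 and also keeps subjects whose withdrawal or loss is dated day 23 or later.

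**Effectiveness set.** "The Completed Cases (CC) population will include all ITT subjects who complete 30-day follow-up" (Protocol 6.6.3). The Protocol adds subjects who have already failed; SAP 3.3 does not repeat that addition. SAP 3.4.1 analyses both primary endpoints on available data without imputation. Resampling from complete lesions and a tipping point analysis are sensitivity analyses there.

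**The concern.** In a drug trial, withdrawal can at least end exposure. Here the only study treatment is over before withdrawal can happen, so leaving the study removes observation alone. The subjects most likely to be withdrawn for health reasons are those who are deteriorating, and they are also the likeliest to have a later MAE or rebleed.

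A hypothetical case shows the mechanism. A subject has symptomatic target-territory ischemia on day 5 that has not led to intervention. That is a secondary endpoint (Protocol 5.3); under Protocol 18 it becomes an MAE only with intervention or death. If the investigator withdraws the subject on day 6 and an intervention follows on day 12, nothing in 8.8 requires that event to be collected. The subject then has no recorded event and no follow-up to day 23, and drops out of both primary analyses.

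If withdrawals lean this way, both observed success rates move upward and safety information is lost for the subjects in whom it matters most.

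**Working it through.** **1. The plan's own figures.** Inputs (Protocol synopsis, 7.4 and 7.9): goals 72% and 82%, anticipated rates 84% and 92%, exact one-sided alpha 0.025, 101 evaluable, 10% attrition.
- Effectiveness: the smallest passing count is 82/101 (exact lower limit 72.2%; 81/101 gives 71.1%). P(X ≥ 82 | 101, 0.72) = 0.0227. Power at 84% is 81.9%. The plan's 101 reproduces.
- Enrollment: 101/0.90 = 112.2, rounded up to 113. This reproduces, and leaves 113 − 101 = 12 lost.
- Safety: the smallest passing count is 91/101 (limit 82.5%), with exact alpha 0.0181 and power 81.6% at 92%.

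**2. Who leaves the primary analyses.**

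| Status at investigator withdrawal | Safety | Effectiveness |
|---|---|---|
| Endpoint event already recorded | stays | stays (Protocol 6.6.3); not repeated in SAP 3.3 |
| No event, day 23 or later | stays (SAP 3.4.1) | depends on whether 30-day follow-up counts as complete |
| No event, before day 23 | leaves | leaves |

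The concern is the last row.

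**3. How many hidden failures overturn a pass.** With all 113 counted, passing needs 91/113 for effectiveness (limit 72.02%; 90/113 gives 71.0%) and 101/113 for safety (82.2%; 100/113 gives 81.1%). If j of the 12 lost subjects are failures, the full count is x + 12 − j.
- Effectiveness, bare pass x = 82: 94 − j ≥ 91 requires j ≤ 3, so 4 failures overturn it. At the expected x = 85, 7 do.
- Safety, bare pass x = 91: 103 − j ≥ 101 requires j ≤ 2, so 3 events overturn it. At the expected x = 93, 5 do.

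**4. False-pass risk under selective withdrawal.** Assumptions: 113 lesions, one per subject; true success p equal to the goal; every withdrawal happens before day 23 and before any event; a fraction L of lesions is lost; failures are k times as likely to leave as successes. Then:
- probability that a success leaves: q = L / (p + k(1 − p)); that a failure leaves: kq;
- success rate among those observed: π = p(1 − q)/(1 − L);
- risk = Σ over m of P(M = m) × P(Bin(m, π) ≥ c(m)), where M ~ Bin(113, 1 − L) and c(m) is the exact critical count for m.

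Example with p = 0.72, k = 2, L = 0.056: q = 0.056/1.28 = 0.0437 and π = 0.72 × 0.9563/0.944 = 0.7293, giving a risk of 3.2%.

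Effectiveness, p = 72% (no loss: 2.5%):

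| Lesions lost | k = 1 | k = 2 | k = 3 | Only failures leave |
|---|---|---|---|---|
| 1.4% | 2.0% | 2.2% | 2.4% | 3.4% |
| 2.8% | 2.0% | 2.5% | 2.9% | 5.7% |
| 4.2% | 2.0% | 2.8% | 3.6% | 9.0% |
| 5.6% | 1.9% | 3.2% | 4.3% | 13.8% |
| 10% | 1.9% | 4.4% | 7.4% | not run |

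In the last column the losses are 5%, 10%, 15% and 20% of failures (0.05 × 0.28 = 1.4%, and so on). The k = 1 column shows that loss unrelated to outcome does no harm. It lies below 2.5% because the exact test is discrete and 113 happens to use nearly all of its alpha.

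Safety, p = 82%, same formula (no loss: 2.2%): 2.2% to 4.0% for k = 2 to 3 at the same 1.4% to 5.6% losses, and 4.1% to 7.0% at 10%. If only future failures leave (20% of them, 0.20 × 0.18 = 3.6% of subjects), 9.9%.

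**The case against.** The other side has a good deal. A final evaluation is required at withdrawal, and 8.8 commits to efforts to retain subjects to day 30. Events recorded before withdrawal still count for safety and, under the Protocol, for effectiveness. SAP 3.4.1 plans a tipping point analysis that turns early-censored lesions or subjects into failures one by one, and Protocol 7.7 plans one over all imputation outcomes. These are aimed at this kind of bias. Health-driven withdrawal may also be rare.

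These safeguards narrow the point without closing it. The final evaluation cannot record later events. The contact attempts listed in 8.8 are for subjects who do not respond, not for those whom the investigator has removed. The tipping point analyses would reveal fragility, but success rests on the primary confidence limits. Resampling from complete lesions assumes missing at random, which withdrawal for worsening health is likely to break.

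Some stronger readings are tempting but unsupported:
- *A device-related event is a separate ground for withdrawal.* The sentence "If the reason for the withdrawal is a device- or procedure-related AE, the event must be reported to the Sponsor" is a reporting duty. It foresees such a reason but grants no further right.
- *The plan orders data collection to stop.* It does not say so. This is inferred from the limit to observations up to withdrawal and the absence of anything later.
- *High-risk subjects in general fall out of both denominators.* Only those withdrawn early and without a recorded event do.
- *The consent form lacks permission for record review.* Its pages were not available, so this cannot be judged.

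**Conclusion.** The gap is real and narrow. A subject whom the investigator withdraws before day 23 without a recorded event is lost to both SAP primary analyses, although the one-time treatment is already complete and the outcome could be learned by telephone or from records.

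Under moderate selection (failures two to three times as likely to leave) the effectiveness false-pass risk is 2.2% to 4.3% at losses of 1.4% to 5.6%, and 4.4% to 7.4% at 10%, against 2.5% with no loss. A reader might take 13.8% as the expected effect. It is a worst case in which no future success is ever withdrawn. The documents give no investigator-withdrawal rate, so the losses and the values of k are assumptions, as is one lesion per subject. Each figure is for one endpoint; the study must pass both, so the risk for the whole study is no larger than that for the failing endpoint.

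This is a cheap improvement worth making, and not a flaw that invalidates the design. SAP 3.3's omission of the Protocol's rule on subjects who have already failed would widen the gap if read literally, but it is a separate discrepancy.

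**What to change.** Add to Protocol 8.8: a subject withdrawn by the investigator, for any reason other than the subject's own withdrawal of consent, stays in follow-up for day-30 ascertainment of vital status, MAEs, rebleeding and reintervention, by telephone or medical-record review. State in Protocol 6.6.3 and 7.7 and in SAP 3.3 and 3.4.1 that such ascertainment counts as 30-day follow-up, so that the subject enters both primary analyses. When a subject withdraws, ask whether record review to day 30 may continue, and record the answer.

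The investigator's right to withdraw a subject need not be deleted; separating it from endpoint ascertainment is enough.

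The cost is protocol and SAP wording, any matching consent language, and some extra chart review at sites. Care does not change and no procedure is added. There is also a gain: if all 113 were ascertained (one lesion each), effectiveness would need 91/113, with exact alpha 0.0247 and power 87.0% at 84%, compared with 81.9% at 101.

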## 9 STUDY MANAGEMENT CONSIDERATIONS

### 9.1 Data Management

The Sponsor and/or assigned designee will be responsible for the quality control of the data. Data will be retained for at least 2 years after the termination/completion of the study or after the approval/withdrawal of the marketing application, whichever occurs later. All other source data, source documents, eCRFs, copies of Protocols and protocol amendments, device accountability forms, correspondence, subject identification lists, informed consent forms, and other essential documents must also be retained for a period of at least 2 years as detailed above. The Sponsor will inform the investigator/institution when these documents are no longer required to be retained.

No study document or image will be destroyed without prior written agreement from the Sponsor. Should the Investigator wish to assign the study records to another party or move them to another location, advance written notice must be given to the Sponsor.

### 9.2 Core Laboratory

An independent core laboratory will be used for the assessment of angiographic endpoints. All protocol-specified imaging studies will be sent to the Core Laboratory for evaluation. Angiographic bleeding absence will be assessed by the Core Laboratory and will supersede the site-determined findings where differences exist. The Core Laboratory interpretations will comprise the primary measures for reporting the primary endpoints and will be used by the CEC as the imaging endpoints for the adjudication of events. The Core Laboratory Imaging Manual will specify details including the image transfer process and imaging endpoint assessment.

### 9.3 Modifications to the Clinical Investigational Plan

No changes from the final approved signed Clinical Investigational Plan (Protocol) will be initiated without the Institutional Review Board's (IRB's) prior written approval of the amendment, except when necessary to eliminate immediate hazards to the subjects or when the change involves only logistics or administration. The Principal Investigator will acknowledge the amendment by signing the new version of the Protocol.

### 9.4 Protocol Deviations

A protocol deviation is the non-adherence to or divergence from the protocol-specific study procedures. For example, deviations from the inclusion and exclusion criteria, deviations from the schedule of required follow-up assessments, improper or lack of consent, and lack of IRB approval, would all be considered protocol deviations.

Subject eligibility for the study is determined by site-measured anatomic criteria; not by core laboratory values. However, enrollment of subjects with core laboratory-determined anatomic measurements on the baseline, pre-interventional angiogram will not be protocol deviations.

#### **9.4.1 Planned Protocol Deviations**

Non-urgent, planned protocol deviations require prior written approval by the Sponsor and, if the deviation affects the scientific soundness of the plan or the rights, safety, or welfare of subjects, prior approval from the IRB and FDA is necessary. A protocol deviation undertaken to protect the life or physical well-being of the patient in an emergency is a special circumstance that needs no prior approval but which must be reported to the Sponsor and the reviewing IRB within 5 working days. The Sponsor must report the deviation to the FDA within 5 working days after the Sponsor learns of the deviation.n No other type of prospective protocol deviation is permitted without prior approval.

#### **9.4.2 Major and Minor Protocol Deviations**

While the FDA does not define major versus minor protocol deviations, the following guidelines will be used in this study. Major deviations will include though divergences from the Protocol that a) affect the rights, safety, and welfare of a study participant, or b) compromise data integrity. Protocol deviations that involve the inclusion or exclusion criteria will be considered major deviations, as will failure to collect primary endpoint data (e.g. as might occur with a missed critical follow-up visit). Out-of-window visits will be considered minor protocol deviations, as will missed non-critical assessments (e.g. laboratory tests not crucial to the primary endpoints or to the subject's safety), and failure to use the proper version of the informed consent form.

#### **9.4.3 Responsibility for Reporting Protocol Deviations**

The Investigator is responsible for the reporting of protocol deviations on the subject's protocol deviation eCRF. When an unreported protocol deviation is identified by the Sponsor or designee through monitoring or other means, the Sponsor or designee will query the Investigator for entry of the deviation. When there remains disagreement between the Investigator and the Sponsor regarding a protocol deviation, the deviation can be considered at a special meeting of the CEC. In this case, the findings of the CEC will prevail.

A record of all protocol deviations will be maintained and reviewed throughout the conduct of the study. The Sponsor will address major or recurrent deviations at a site and take appropriate corresponding action. Continued non-compliance with the Protocol may lead to termination of the Investigator's or the investigational site's participation in the study.

### **9.5 Information to Study Personnel**

The Investigator is responsible for providing study information to all research staff members involved in the study or in any element of subject management, both before starting the study procedures and during the course of the study (e.g., when new staff become involved). The Investigator must ensure

---

n Procedures for reporting deviations from the investigational plan are outlined in 21 CFR 812.150.

---

that all study staff members are qualified by education, experience, and training to perform their specific responsibilities.

The Sponsor representative and/or designee, e.g. a representative of its Contract Research Organization (CRO), is responsible for explaining the Protocol to all study staff, including the Investigator, and for assessing their compliance with the Protocol throughout the study. Additional information may be made available during the study when new staff become involved in the study, and as otherwise agreed upon with the Investigator.

## 10 ASSESSMENT OF SAFETY

### 10.1 Defining Adverse Events

An adverse event is an untoward medical occurrence or exacerbation of an existing medical condition subsequent to the experimental therapy. Adverse events are categorized in several ways:

#### Severity

- **Mild:** No limitation of usual activities, no therapy or only symptomatic therapy required to treat the injury or illness.
- **Moderate:** Some limitation of usual activities or specific therapy is required.
- **Severe:** Inability to carry out usual activities, hospitalization, emergency treatment, life threatening events, or death.

#### Anticipated versus Unanticipated

- Anticipated
- Unanticipated

#### Relatedness

- Device-related
- Procedure-related

The relationship to the device or to the procedure is classified by the following levels of certainty:

- **Unrelated:** The clinical event is completely independent of study procedure/study device and/or evidence exists that the event is definitely related to another etiology.
- **Possibly related:** The clinical event occurs within a reasonable time sequence to study procedure/study device and there is some evidence to “possibly” suggest a causal relationship. However, the influence of other factors such as underlying disease, concomitant medications, or concurrent treatment may have contributed to the event.

- **Definitely related:** The clinical event occurs in a plausible time relationship to study procedure/study device and cannot be explained by any concurrent disease or other devices, drugs or chemicals.
- **Relationship unknown:** The relationship to the study procedure/study device is not known.

### **Seriousness**

Adverse events will be categorized as either serious or non-serious. A Serious Adverse Event (SAE) is an event that meets at least one of the following:

- Is fatal
- Is life-threatening
- Results in persistent or significant disability/incapacity
- Results in permanent impairment of a body function or permanent damage to a body structure
- Results in hospitalization or prolongs a hospitalization
- Necessitates medical or surgical intervention to preclude permanent impairment of a body function or permanent damage to a body structure

### **Major Adverse Event (MAE)**

MAEs comprise a subcategory of adverse events defined for this clinical study. MAEs include any of the primary safety endpoint components, as defined in **Section 5.1**, above.

### **Unanticipated Adverse Device Effect (UADE)**

An UADE is defined as “any serious adverse effect on health or safety or any life-threatening problem or death caused by, or associated with, a device, if that effect, problem, or death was not previously identified in nature, severity, or degree of incidence in the investigational plan or application (including a supplementary application), or any other unanticipated serious problem associated with the device that relates to the rights, safety, or welfare of subjects.” **Section 15.1** (below) includes a list of possible adverse events associated with the study device and the index procedure, including those events considered major device-related events and major morbidity. UADE are reportable at all time points throughout the trial and require submission to the Sponsor. The Investigator must report UADEs to the Sponsor within 2 business days of learning of the event.o

